Approximately 20 male and female subjects aged 18 to 80 years who present with a primary diagnosis of bipolar disorder type 1 currently in a major depressive episode (i.e. bipolar depression) and taking at least one mood stabilizer will receive open label treatment with sTMS. Furthermore, subjects will also complete weekly EEGs and some of the subjects will complete baseline and follow-up brain fMRI. Eligible subjects must provide written informed consent, be capable of comprehending the nature of the study, and be considered by the Investigator as likely to comply with the visit schedule. Subjects will be recruited from self-referral, clinician referral, and through contacts with the Mood Disorders Research Program. Additional inclusion/exclusion criteria are listed below.

C2. Study Design

This clinical trial is a prospective, open label, single center study (Butler Hospital). This study is designed to evaluate the safety and effectiveness of sTMS for symptoms of major depressive episode in subjects with bipolar disorder type I. A total of 20 subjects will receive 5 daily treatments per treatment week for 6 treatment weeks (total of 30 treatments) or when remission is achieved.

After providing written informed consent, subjects will start the assessment phase. Subjects must be on a stable dose of at least one mood stabilizer for at least 4 half-lives. Subjects will be assessed using clinician based interviews and self-rating scales (to determine baseline clinical characteristics). Subjects will also complete a baseline EEG.

Treatment will be initiated on Day 1 of the study and will be delivered daily for 6 weeks or when remission is achieved. Remission will be defined by Inventory of Depressive Symptomatology, Self-

Report Version (IDS-SR) score <14 for at least 14 calendar days. Subjects will be evaluated at the end of each treatment week during the treatment period.

At the end of each treatment week, subjects will repeat self-rating scales (see study flow chart, below).

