A subset of the subjects will also complete a baseline and follow-up fMRI to investigate brain functioning (pending additional funding to support the scans); participation in the brain imaging at baseline and at endpoint will be optional. fMRI procedures will consist of a one hour session in the scanner during which subjects will complete protocols for assessing resting state, emotional processing, and reward processing, which are considered core components of bipolar disorder psychopathology. fMRI procedures will occur within one week of baseline assessments and study endpoint.

The end point assessments will be completed within 5 days of the final treatment day. In final evaluation, subjects will be assessed using clinician-based interviews and self-rating scales to evaluate efficacy of the treatment. Side effects will be recorded as described by study participants at any visit or during any contact with the subjects.

Two weeks after the last sTMS treatment, subjects will be contacted by telephone for a brief follow-up safety assessment

C3. Specific Procedures or Treatments

C3a. Open Label Trial:

This study is an open label pilot study, to determine effect size for sample estimation, and determine safety and preliminary efficacy. Subjects will start treatment after baseline assessments are completed; treatment will continue for 6 treatment weeks (or until subject remits per IDSSR criterion score sustained for 14 days). A treatment week will consist of 5 treatment days within 8 calendar days. Furthermore, all subjects must have at least 5 treatments within 10 calendar days; and 30 treatments within 6 treatment weeks (plus 3 days grace period), which will lead to 45 calendar days.

Study Occasion – Open Label, not sham controlled												
Rating or procedure	Assessment Phase			Treatment Phase (week)						Termination Phase		
	Screening	MRI	Baseline	1	2	3	4	5	6	MRI	End Point	Phone Check-in
CONSENT/ELIGIBILITY	X											
SCID-5-RV	X											
Consent/MRI	X											
EEG: IAF	x											
CTQ	x											
HRSD/MADRS	X		X								X	
YRMS	X		X								X	X
BAS/BIS			X								X	
PCGI-I											X	
CGI-Bipolar			X	X	X	X	X	X	X		X	X
IDS-SR		X	x*	X	X	X	X	X	X	x*	X	
ASRM		X	x*	X	X	X	X	X	X	x*	X	
PHQ9		X	x*	X	X	X	X	X	X	x*	X	
EEG: Resting			x								X	
MRI – resting state, cerebral blood flow, reward processing, emotion processing, cognitive processing		X								X		

x* Baseline measures repeated, if needed only if >3 days from MRI or first treatment

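### Does the 45-day treatment period in C3a contradict the plan's own 8-day treatment week?

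*Combined protocol and SAP*

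**What the plan says.** Section C2 (Study Design) describes the course as "5 daily treatments per treatment week for 6 treatment weeks (total of 30 treatments", and further on says that treatment "will be delivered daily for 6 weeks or when remission is achieved". Section C3a (Open Label Trial) repeats that "treatment will continue for 6 treatment weeks", unless the subject remits sooner, and then sets three limits on timing:

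- per treatment week: "A treatment week will consist of 5 treatment days within 8 calendar days";
- a minimum rate: "all subjects must have at least 5 treatments within 10 calendar days";
- the whole course: "30 treatments within 6 treatment weeks (plus 3 days grace period), which will lead to 45 calendar days".

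Two later contacts depend on when treatment ends. Both are in C2: "The end point assessments will be completed within 5 days of the final treatment day", and "Two weeks after the last sTMS treatment, subjects will be contacted by telephone for a brief follow-up safety assessment".

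Section C4 (Data Analysis) takes change in IDS-SR, HRSD and MADRS from baseline to End Point, with response and remission based on the IDS-SR. It does not refer to the length of the course in calendar days.

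**The concern.** C3a defines a treatment week with an 8-day span and, one sentence later, uses the same term to arrive at 45 days. A reader who carries the definition forward gets 51 days and concludes that one of the figures is wrong. The text says that the count leads to 45, which sounds like a derived total, and it nowhere calls 45 a maximum.

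If the figures did conflict, a session given on days 46 to 51 could be counted as within the plan or as a deviation, depending on the reader. A subject with missed sessions might then receive fewer or more of the 30, and the latest possible dates for the End Point visit and the phone check would move.

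**Working it through.** **Inputs.** From C3a: 6 treatment weeks, 5 sessions in at most 8 calendar days, at least 5 sessions in 10 calendar days, 3 grace days, and a stated total of 45 days. From C2: 6 weeks of treatment, End Point within 5 days of the last session, phone check 14 days after it.

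**The plan's own figure.** Total = weeks × days per week + grace.

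| Length taken for a week | Calculation | Total (days) |
|---|---|---|
| 7 days | 6 × 7 + 3 | 45 |
| 8 days, windows sharing a boundary day | 6 × 7 + 1 + 3 | 46 |
| 8 days, windows back to back | 6 × 8 + 3 | 51 |
| 10 days, windows back to back | 6 × 10 + 3 | 63 |

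Of these, only the 7-day week gives 45, and it gives it exactly. The stated figure is therefore correct for calendar weeks, which is how C2 describes the course.

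**Where 51 comes from.** An 8-day window is the longest span allowed for five sessions; it is not a fixed week length. To reach 51, every one of the six windows must be used in full, each must start only after the previous one has closed, and the grace days must be added on top. The plan does not say that the tolerances accumulate in this way.

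**Can all the limits hold together?** Yes, if 45 is an overall limit. Starting from 6 × 7 = 42 days, the 3 grace days let up to three treatment weeks run to an eighth day: 42 + 3 = 45. The 10-day rule fits the same pattern, since 7 + 3 = 10 is one ordinary week plus the same 3 days. That last link is my inference; the document does not state it.

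**Who is affected.** Assume weekday-only treatment, which the documents do not state. With a Monday start and no missed session, the 30th session falls on day 5 × 7 + 5 = 40. With a start on Tuesday to Friday, each run of five weekdays takes 7 days, so the 30th session falls on day 6 × 7 = 42. Both lie inside 45 and inside 51.

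**Effect on later contacts.** The latest End Point visit is day 45 + 5 = 50 or day 51 + 5 = 56. The latest phone check is day 45 + 14 = 59 or day 51 + 14 = 65. Each moves by 51 − 45 = 6 days at the extreme. Both are counted from the actual last session, so they stay defined on either reading.

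**Effect on the analysis.** C4 compares baseline with End Point and defines no analysis set, covariate or visit window that depends on day 45 or day 51. The sample size of 20 is not derived from the treatment period. The remission rule in C2, which can end treatment early, counts 14 calendar days and does not use the length of the course.

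**The case for a change.** The strongest case for a correction is that the plan defines a term and then appears not to use it. Six 8-day windows come to 48 days, which exceeds 45 before any grace day is added, and the wording presents 45 as a consequence of the count. If 45 is a limit, staff have to work out for themselves that no more than three weeks can use the eighth day. The 10-day rule adds a third window, and its relation to the other two is not explained. A clearer sentence would cost almost nothing.

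The observation about wording stands: 45 is not labelled as a limit, and the three windows are not tied together. The claim of an arithmetic error does not stand. The sentence that contains 45 sets out what every subject must complete, and within what period, so a limit is its natural sense, and under that sense nothing in C3a conflicts. The case for correction also shows no result that would differ. It rests on a tidier classification of late sessions for subjects who miss appointments.

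**Conclusion.** No change to the plan is needed. The 45 days reproduce exactly from ordinary weeks plus the grace period and agree with C2. The 8-day figure can be read beside it as a weekly tolerance. What remains is loose wording, worth at most 6 days (51 against 45), and only for a subject whose course slips beyond day 45. The endpoints, the sample size and every analysis in C4 are the same on either reading, and the follow-up contacts remain defined.

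This rests on reading the clause as a requirement with 45 as its limit, which the wording allows but does not state. The statement that an uninterrupted course ends by day 42 also assumes weekday-only sessions. How a late session is classed is for the investigators to decide, and I take no position on which window should govern.

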Uploaded to ClinicalTrials.gov 14 Feb 2020

Clinicaltrials.gov Record Summary Documents Cover Page (IRB Approved 12/13/2017)

NeoSync TMS Treatment for Bipolar I Depression (NCT02839798)

Attached document is protocol with statistical analysis plan as approved by Butler IRB.

The study had no external funding (investigational devices provided by the company Neosync, which no longer exists). This pilot trial was stopped early due to lack of funding.

IRB # 1601-004

**BUTLER HOSPITAL
INSTITUTIONAL REVIEW BOARD
PROTOCOL**

ATTENTION:

*Before completing this protocol, go to the Butler IRB Forms library on IRBNet and Download the most recent version. Consult the **IRB Guidelines** for updated directions.*

TITLE OF PROJECT: Evaluation of NeoSync EEG Synchronized TMS For the Treatment of Major Depressive Episode in Bipolar Disorder and Associated Neural Response: An Open Label Trial

Principal Investigator (PI): [name]

Other Investigator(s): [name] MD,

Description of Study

A. Specific Aims

The objective of this study is to establish the safety and preliminary efficacy of Synchronized Transcranial Magnetic Stimulation (sTMS) treatment, for subjects with Bipolar Disorder type I (BD-I) in a major depressive episode (BDD – bipolar depression, hereafter).

B. Background

Bipolar disorder is one of the top ten most debilitating of all illnesses. Two reports from the NIMH Collaborative Depression Study demonstrated that individuals with bipolar disorder experience depression much more frequently than hypomania or mania (Judd et al. 2002; Judd et al. 2003; Judd et al. 2012). Specifically, in these studies the hallmark symptoms of bipolar disorder (i.e. hypomanic or manic symptoms) occurred only during 9% of the time in individuals with BD-I, and in only 1% of the time in individuals with BD-II. During the depressed phase of bipolar disorder illness, affected individuals present with depressed mood, loss of interest or pleasure, feelings of guilt, low self-worth, disturbed sleep or appetite, low energy, and poor concentration.

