On the other hand, the efficacy of rTMS for bipolar depression has not been widely investigated. From this perspective, a number of open label studies showed positive effect for rTMS (with a mixed range of parameters) in depressed patients with BDD (Dell'Osso et al. 2009; Cohen et al. 2010; Harel et al. 2011), and such result has been confirmed in few double-blind, sham-controlled studies with limited samples (Dolberg et al. 2002; Nahas et al. 2003; Tamas et al. 2007). Two of these studies were limited by small samples. Dolberg investigated a sample on 20 individuals with bipolar depression, ten in each arm (TMS parameters were not reported). In comparison, Tamas studied 5 individuals with bipolar depression (one in the sham arm and 4 in the active arm – 1Hz right frontal cortex). Nahas treated a mixed sample of 23 individual with bipolar 1 and 2, while in depressed / mixed episode (12 in the sham arm and 11 in the active arm – 5Hz left frontal cortex). However, there are case reports indicating mood destabilization leading to a manic episode after TMS treatment (Dolberg et al. 2001). It is still up to debate if rTMS using standard protocols are safe to be used in bipolar disorder.

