A total of 20 subjects will be enrolled and treated. The sample size for this open-label study is based on estimations regarding the appropriate amount of information required to inform next steps in trial design rather than on statistical significance calculations for any primary safety or efficacy endpoint. For the primary efficacy endpoint, we will analyze change in total scores on the IDS-SR, HRSD, and MADRS scores from baseline to End Point. Categorical response (50% decrease from pre-treatment baseline on IDS-SR) and Remission (IDS-SR score <14) will be calculated to determine treatment efficacy.

Neuroimaging data will be pre-processed and analyzed using statistical parametric mapping software SPM5 (<http://www.fil.ion.ucl.ac.uk/spm>). For both experiments, a first-level effect model will be constructed with conditions entered separately in the design matrix.

D. Material Inducements

Subjects will not be compensated for the sTMS treatment but rather receive it free of charge. Subjects that participate in each neuroimaging session will receive a gift card with value of \$25 for each MRI scan they complete.

E. Training of Research Personnel

Clinical data will be collected, entered and analyzed by [name] in the Mood Disorders Research Program and research assistants trained under his supervision. Neuroimaging data will be processed and analyzed by [name] and research assistants trained under his supervision. [name] will provide overall supervision and oversight for the study.

3) Human Subjects**A. Subject Population** *(include number; gender; age; diagnosis; inpatient vs. outpatient; physical health; inclusion/exclusion criteria; rationale for use of special groups)*

A total of 20 male and female subjects, age 18 to 80 years, who are suffering from bipolar disorder type 1, currently depressed, will be enrolled into the study and treated. All subjects will receive open label sTMS treatment. Subjects will be recruited from outpatient setting and in stable physical health.

Inclusion Criteria: Subjects must meet all of the following inclusion criteria to qualify for enrollment into the study:

- (1) 18 – 80 years of age;
- (2) DSM-5 primary diagnosis of Bipolar Disorder type 1 (with a documented diagnosis of the disorder on medical record), currently in a Major Depressive Episode by diagnostic criteria elicited by structured clinical interview (SCID-5-RV);
- (3) MADRS score ≥ 20 ;
- (4) Duration of current episode ≥ 4 weeks
- (5) YMRS score ≤ 12 ;

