The alternatives to participation in this study: (1) not receiving treatment for bipolar depression, or (2) receiving standard treatment administered by a clinician and/or prescribed by a physician or nurse outside of this research study. The primary risk of untreated BDD is prolonged disability and suffering, or if the condition becomes severe/worsens, possibly attempting or completing suicide. Risks related to obtaining treatment for depression outside of this study are the ones typically associated with available antidepressant and mood stabilizer pharmacotherapies, somatic therapies, or psychotherapy (side effects unique to each), and the risk of non-response to treatment interventions.

D. Protection of the Subject (include: D.1. measures to minimize potential risks; D.2 measures to ensure confidentiality; D.3. data safety monitoring plan)

D1. Measures to minimize potential risks:

Risk of Mood Destabilization: As part of inclusion criteria, subjects are required to receive stable and therapeutic doses of mood stabilizers, which should minimize TMS related mood destabilization. Furthermore, sTMS is potentially well suited to be used in bipolar disorder due to the relatively low intensity of stimulation, compared to standard rTMS. The magnetic field generated by sTMS is approximately only 10% of conventional TMS output. Moreover, in comparison, the total amount of magnetic field exposure for a full course of sTMS therapy is approximately only a minimal fraction of the exposure from a single scan with an MRI, which is widely used to study brain function in the psychiatric population, including children and infants. Furthermore, mood stability will be assessed weekly with Altman Self-Rating Mania Scale as a screening tool, and values above 6 on that screening scale will prompt further clinical evaluation that will include assessment with YRMS. Subjects will also be assessed weekly with self-rating scales for depression.

Risk of Side Effects from sTMS: A trained member of the research staff will administer each treatment and be present throughout treatment sessions to observe the participants. Moreover, all procedures will occur as part of the Butler Hospital's neuromodulation clinic, and a physician will be available at all times during treatments. Serial assessments side effects and contacts with research staff and study physicians will be used to identify and address any treatment-emergent side effects.

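### Response and remission in C4 rest on the IDS-SR alone, so a subject whose depression score falls through a switch into hypomania or mania can be counted as an efficacy success

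*Combined protocol and SAP*

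**What the plan says.** C4 names change on three depression scales (IDS-SR, HRSD and MADRS) as the primary efficacy endpoint, then adds two categorical outcomes: "Categorical response (50% decrease from pre-treatment baseline on IDS-SR) and Remission (IDS-SR score <14) will be calculated to determine treatment efficacy". It describes no analysis of the ASRM, YMRS or CGI-Bipolar. It does not define treatment-emergent mania or hypomania, and it does not say how a subject who switches is classified for efficacy.

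Other sections treat mania as a concern. B. Background notes that "there are case reports indicating mood destabilization leading to a manic episode after TMS treatment", and presents sTMS as possibly carrying less of this risk. Section 3, C. Potential Risks opens with mood destabilization. D1 sets up a weekly ASRM screen, where "values above 6 on that screening scale will prompt further clinical evaluation that will include assessment with YRMS" (the protocol spells the scale both YRMS and YMRS).

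The schedule in C3a places the ASRM at weeks 1 to 6 and End Point, the CGI-Bipolar at the same visits, and the YMRS at Screening, Baseline, End Point and the phone check-in. Entry requires "YMRS score ≤ 12".

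**The concern.** A depressive episode in bipolar I disorder can end in recovery or in a switch of polarity, and a depression self-rating alone cannot tell these apart. Take a hypothetical subject whose IDS-SR falls from 40 to 10 while the ASRM is above 6 and the YMRS above 12. The fall is (40 − 10)/40 = 75% and the final score is below 14, so C4 makes this subject both a responder and a remitter, although the mania scales show a switch.

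C3a says the pilot is meant to supply an effect size for planning a later trial. With one open-label arm, no comparator rate carries the same error and offsets it. If some of the reported response or remission reflects switching, the rates carried forward overstate recovery from depression.

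**Working it through.** **Inputs from the documents**
- Subjects: "A total of 20 subjects will be enrolled and treated" (C4), one arm.
- Basis for that number: C4 rests it on the information needed for the next trial "rather than on statistical significance calculations for any primary safety or efficacy endpoint". There is no power calculation to reproduce.
- Response: a 50% fall on the IDS-SR. Remission: IDS-SR below 14. C4 names no visit for these; I take End Point, as for the primary endpoint.

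**Assumed, because the documents give no figure**
- Probability p that a subject switches during the study: 2% to 15%.
- Subjects who meet the criterion without a switch: 4, 6 or 8 of 20.

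**Step 1. Does any rule remove a switched subject from the efficacy count?** C4 contains none. D1 leads from a raised ASRM to a clinical evaluation with the YMRS and stops there. A switch can therefore be detected without changing the efficacy classification.

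**Step 2. Effect of one subject.** 1/20 = 5 percentage points. The cover page says the trial stopped early; with n below 20 analysed, the effect is 1/n and so larger.

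**Step 3. Effect on the reported rate.** Two switched subjects who also meet the IDS-SR criterion, with exact (Clopper-Pearson) 95% limits:

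| Meet criterion without switch | Switch counted as failure | C4 as written |
|---|---|---|
| 4 | 4/20 = 20% (5.7% to 43.7%) | 6/20 = 30% (11.9% to 54.3%) |
| 6 | 6/20 = 30% (11.9% to 54.3%) | 8/20 = 40% (19.1% to 63.9%) |
| 8 | 8/20 = 40% (19.1% to 63.9%) | 10/20 = 50% (27.2% to 72.8%) |

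**Step 4. How likely is any switch?** Expected number = 20p. P(at least one) = 1 − (1 − p)^20. P(at least two) = 1 − (1 − p)^20 − 20p(1 − p)^19.

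| p | Expected switches | P(at least one) | P(at least two) |
|---|---|---|---|
| 2% | 0.4 | 33% | 6% |
| 5% | 1.0 | 64% | 26% |
| 10% | 2.0 | 88% | 61% |
| 15% | 3.0 | 96% | 82% |

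**Step 5. From switch to misclassification.** Let q be the probability that a switched subject meets the IDS-SR criterion while the mania signal is present. The expected inflation is 20pq/20 = pq, and the chance of at least one misclassified subject is 1 − (1 − pq)^20. Since q is at most 1, the Step 4 figures are upper limits for each assumed p, and the expected inflation is at most 2 to 15 percentage points. The documents give no information on q.

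**The case against.** The strongest reply has four parts.

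1. A switch does not by itself make a success: the IDS-SR must also fall by half or below 14. The documents do not show how that scale behaves in mania. This stands, and it is why the point says *can be counted*.
2. The categorical outcomes supplement a primary endpoint of change on three scales, two of them clinician-rated. No success threshold exists for a 5-point shift to cross. At the low end of the assumed range, two or more switches have only a 6% chance. This limits the importance of the point. But C4 says the categorical rates will be used to judge efficacy, and the primary scales also measure only depression.
3. Mania is watched closely, with weekly ASRM and CGI-Bipolar ratings, YMRS at End Point and the phone check-in, and weekly staff meetings that cover adverse events. Among 20 open-label subjects, an overlap of switch and response would probably be noticed. That concerns detection; no text carries it into the reported rates.
4. Reporting efficacy and safety separately is a legitimate choice for a pilot, and the plan has no cut-off written to define a switch. The YMRS limit of 12 is an entry criterion, and an ASRM above 6 only prompts evaluation. This stands as a cost of the fix, and is a reason to show both rates.

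**Conclusion.** The point holds as a defect in the stated definitions of response and remission. Each switched subject who meets the IDS-SR criterion adds 5 percentage points at n = 20. Under assumed switch rates of 2% to 15%, the chance of at least one switch is 33% to 96%, an upper limit on the chance of any misclassification. The gap in the definitions does not depend on those assumptions; its likely size does. The exact intervals in the working are far wider than the shift, so the matter is what the rate means, more than its precision.

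Four stronger readings are tempting, and the documents do not support them.
- *The safety result is biased too.* The switch would still be recorded through the ASRM, the YMRS and adverse-event review. Only the efficacy rates are affected.
- *The Background figure gives the switch rate.* The statement that manic or hypomanic symptoms "occurred only during 9% of the time in individuals with BD-I" describes a share of time with symptoms. It is neither a switch incidence over six weeks nor a bound on switching caused by a device.
- *The rule ending treatment contradicts the mania monitoring.* C3a continues treatment for the planned weeks or "until subject remits per IDSSR criterion score sustained for 14 days", while the weekly ASRM screen runs alongside. The two can coexist, and no conflict is shown.
- *Switching is the trial's main safety failure.* The protocol names no primary safety endpoint. It lists mood destabilization beside non-response and worsening depression.

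**What to change.** In C4, for analysis only, define response and remission as the IDS-SR criterion **and** no mania signal at the same assessment:

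- at End Point, YMRS not above 12;
- at weekly visits, if the outcomes are also computed there, ASRM not above 6 or, if above 6, the triggered YMRS not above 12.

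Count subjects who do not meet both parts as non-responders and non-remitters. Report the IDS-SR-only rate beside the new one, so that the difference is visible and nothing is lost. State in advance how a raised ASRM without a timely YMRS is handled, since D1 does not say when the triggered rating takes place.

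This changes no visit, treatment or monitoring procedure and needs no new scale. It can be applied to data already collected.

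The costs are a slightly lower reported response and remission rate, and a YMRS cut-off borrowed from eligibility. Two limits remain. A switch that resolves before End Point does not alter the End Point classification, although it stays in the safety record. The primary endpoint of change on the three depression scales is left as it is.
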